### **3.5.7.4 Assessment of Severity of Unsolicited Adverse Events**

The severity (or intensity) of an AE refers to the extent to which it affects the subject's daily activities and will be classified as mild (Grade 1), moderate (Grade 2), severe (Grade 3), or potentially life threatening (Grade 4) using the following criteria:

- Mild (Grade 1): These events do not interfere with the subject's daily activities.
- Moderate (Grade 2): These events cause some interference with the subject's daily activities but do not require medical intervention.
- Severe (Grade 3): These events prevent the subject's daily activity and require medical intervention.
- Life threatening (Grade 4): These events require an emergency room visit or hospitalization.

Changes in the severity of an AE should be documented to allow an assessment of the duration of the event at each level of intensity to be performed. An AE characterized as intermittent requires documentation of onset and duration of each episode.

The Toxicity Grading Scale for Healthy Adult and Adolescent Volunteers Enrolled in Preventative Vaccine Clinical Trials ([CBER 2007](#)) will be used to categorize solicited

reactogenicity, safety laboratory test results, and vital sign measurements observed during this study. Specific criteria for clinical and laboratory abnormalities are presented in [Table 6-3](#) and [Table 6-4](#), respectively, and will be graded if outside of the reference range for the laboratory utilized. Of note, the laboratory test value itself may not be the AE classification. Each AE will be classified by its most specific term (eg, renal insufficiency, bronchitis) and supporting evidence (eg, laboratory test value, x-ray) will not be classified as an AE per se.

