A urine screen for drugs of abuse will be performed by the local laboratory at Screening and before dose administration at Visit 1 for opiates, cocaine, phencyclidine, amphetamines, benzodiazepines, and methadone (cannabis excluded).

Should safety laboratory testing at 7 days post-vaccination result in a Grade 2 or greater toxicity score, then repeat testing within the next 10 days must occur and this may include an unscheduled visit. Should the subject's laboratory test value not return to Baseline then periodic testing may be needed until the abnormality is deemed to be associated with a new stable AE or determined to be not clinically significant by the investigator.

Those values that fall within the normal range of the laboratory will automatically be classified as normal and receive a toxicity score of 0. All values that have a toxicity score of Grade 1 or greater will also be evaluated by the investigator and classified as “abnormal clinically significant (CS)”, or “abnormal not clinically significant (NCS).” Investigators should use their clinical judgment when considering the clinical significance of any abnormal laboratory findings. All laboratory test values with a toxicity score of Grade 3 or greater will be entered as AEs. Any additional laboratory test value that is determined to be clinically significant will also be recorded as an AE, should that be considered the primary diagnosis. In such instances, the abnormal value and grade will be documented on the AE page of the eCRF. The investigator will continue to monitor the subject with additional assessments until the values have reached the reference range or the values at Screening or until the investigator determines that follow-up is no longer medically necessary. The only exception to this rule would be a laboratory test value that is associated with an identified ongoing AE where that event would be the classifying AE.

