Childbearing potential defined as any female who has experienced menarche and who is NOT permanently sterile or post-menopausal. Post-menopausal is defined as 12 consecutive months with no menses without an alternative medical cause.

Note: X/Xc denotes being performed before and after vaccination.

- a Visit 3a will comprise of sentinel cohort only.
- b To confirm post-menopausal status, as needed.
- c Serology testing will include hepatitis B surface antigen, hepatitis C virus antibody, and human immunodeficiency virus type 1 and 2 antibodies.
- d At Screening, if the subject has no proof of yellow fever vaccination within 20 years, or other documentation of flavivirus status, the West Nile virus screening test will be administered. West Nile virus serology screen can occur up to 90 days prior to randomization.
- e Urine drug screen for drugs of abuse will be performed at Screening and before dose administration at Visit 1 for opiates, cocaine, phencyclidine, amphetamines, benzodiazepines, and methadone (cannabis excluded).
- f Full physical examination at Screening; symptom-directed (targeted) physical examination at all other scheduled time points. Interim physical examinations will be performed at the discretion of the investigator, if necessary. Height and weight will be measured and body mass index calculated at Screening only.
- g Vital sign measurements (systolic and diastolic blood pressures, heart rate, respiratory rate, and body temperature) at Visit 1 and Visit 4 will be collected once before dose administration and at least 60 minutes after dose administration (before subjects are discharged).
- h Safety laboratory test values include hematocrit, hemoglobin, mean corpuscular hemoglobin, mean corpuscular hemoglobin concentration, mean corpuscular volume, platelet count, red blood cell count, total and differential white blood cell count, alanine aminotransferase, alkaline phosphatase, aspartate aminotransferase, amylase, lipase, bilirubin (total and direct), blood urea nitrogen, creatinine, random glucose, potassium, sodium, total protein, calcium, albumin, prothrombin time, partial thromboplastin time.
- i A subset of safety laboratory test values for albumin, bilirubin (total and direct), prothrombin time, partial thromboplastin time, alkaline phosphatase, alanine aminotransferase, aspartate aminotransferase.

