### 6.3 Appendix 3: Toxicity Grading Scale Tables

The toxicity grading scales for clinical and laboratory abnormalities are presented in [Table 6-3](#) and [Table 6-4](#), respectively. Note that for laboratory abnormalities, grading only occurs if the values reside outside of the normal values established by the clinical laboratory. For study-specific laboratory normal ranges and associated toxicity grades, refer to the laboratory manual.

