Source: Guidance for industry – Toxicity grading scale for healthy adult and adolescent volunteers enrolled in preventative vaccine clinical trials; Tables for laboratory abnormalities (CBER 2007).

Hematology *	Mild (Grade 1)	Moderate (Grade 2)	Severe (Grade 3)	Potentially Life Threatening (Grade 4)
Hemoglobin (female) (g/dL)	11.0 – 12.0	9.5 – 10.9	8.0 – 9.4	< 8.0
Hemoglobin (female) change from baseline value (g/dL)	Any decrease – 1.5	1.6 – 2.0	2.1 – 5.0	> 5.0
Hemoglobin (male) (g/dL)	12.5 – 13.5	10.5 – 12.4	8.5 – 10.4	< 8.5
Hemoglobin (male) change from baseline value (g/dL)	Any decrease – 1.5	1.6 – 2.0	2.1 – 5.0	> 5.0
WBC increase (cell/mm  )	10800 – 15000	15001 – 20000	20001 – 25000	> 25000
WBC decrease (cell/mm  )	2500 – 3500	1500 – 2499	1000 – 1499	< 1000
Lymphocytes decrease (cell/mm  )	750 – 1000	500 – 749	250 – 499	< 250
Neutrophils decrease (cell/mm  )	1500 – 2000	1000 – 1499	500 – 999	< 500
Eosinophils (cell/mm  )	650 – 1500	1501 – 5000	> 5000	Hypereosinophilic
Platelets decreased (cell/mm  )	125 000 – 140 000	100 000 – 124 000	25000 – 99000	< 25000
PT; increase by factor	1.0 – 1.10 × ULN	1.11 – 1.20 × ULN	1.21 – 1.25 × ULN	> 1.25 × ULN
PTT; increase by factor	1.0 – 1.2 × ULN	1.21 – 1.4 × ULN	1.41 – 1.5 × ULN	> 1.5 × ULN

Abbreviations: PT, prothrombin time; PTT, partial thromboplastin time; ULN, upper limit of normal; WBC, white blood cell.

\* The laboratory values provided in the tables serve as guidelines and are dependent upon institutional normal parameters. Institutional normal reference ranges should be provided to demonstrate that they are appropriate.

[figure not shown]
Source: Guidance for industry – Toxicity grading scale for healthy adult and adolescent volunteers enrolled in preventative vaccine clinical trials; Tables for laboratory abnormalities ([CBER 2007](#)).

Urine *	Mild (Grade 1)	Moderate (Grade 2)	Severe (Grade 3)	Potentially Life Threatening (Grade 4)
Protein	Trace	1+	2+	Hospitalization or dialysis
Glucose	Trace	1+	2+	Hospitalization for hyperglycemia
Blood (microscopic) – red blood cells per high power field (rbc/hpf)	1 – 10	11 – 50	> 50 and/or gross blood	Hospitalization or packed red blood cells transfusion

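### A hemoglobin fall of 2.1 g/dL or more that ends inside the normal range scores 0, so none of the score-based safety steps applies to it

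*Protocol*

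**What the plan says.** The in-range rule appears three times in the protocol. Section 3.5.8: "Those values that fall within the normal range of the laboratory will automatically be classified as normal and receive a toxicity score of 0". Section 3.5.7.4 says that laboratory abnormalities "will be graded if outside of the reference range for the laboratory utilized". Section 6.3, which introduces the grading tables, says that "grading only occurs if the values reside outside of the normal values established by the clinical laboratory".

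The hematology part of Table 6-4 grades hemoglobin in two ways, by absolute value and by change from baseline. The female change row begins "Hemoglobin (female) change from baseline value (g/dL", and the male row has the same cut-offs: any decrease up to 1.5 g/dL is Grade 1, 1.6 to 2.0 Grade 2, 2.1 to 5.0 Grade 3, and above 5.0 Grade 4. No other analyte has a change row. Section 3.1 sets the pre-vaccination value at Visit 1 as the baseline.

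Several steps then depend on the score. In Section 3.5.8, a Grade 2 or higher score at Day 7 means "then repeat testing within the next 10 days must occur". On clinical significance: "All values that have a toxicity score of Grade 1 or greater will also be evaluated by the investigator". On adverse events: "All laboratory test values with a toxicity score of Grade 3 or greater will be entered as AEs". Section 3.4.2.1 gives the SMC laboratory toxicity scores through Visit 5 for escalation. Section 3.4.2.2 pauses a cohort on two or more Grade 3 or higher scores for the same test, if judged potentially vaccine related.

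**The concern.** A change row is there to catch a large drop in someone who started high, whose later value may not look abnormal. The in-range rule switches the row off for the part of that group whose later value is still within limits. Grades can then run in the wrong order: a larger fall scores 0 and a smaller one Grade 3.

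At stake is whether a marked fall is repeated, recorded and shown as Grade 3 to those deciding on further dosing. This is a first-in-human escalation with 30 subjects per cohort, and two Grade 3 scores are enough to trigger the pause rule.

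**Working it through.** The plan states no figure on this point, so there is none to reproduce.

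**1. Scoring under the rules as written.** Assumed lower limits of normal: 13.5 g/dL (men) and 12.0 g/dL (women). The documents give none. Where the absolute and change rows both apply, I take the higher grade.

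| Visit 1 to later value (g/dL) | Fall | Change-row grade | In range? | Score |
|---|---|---|---|---|
| Man, 17.0 to 13.5 | 3.5 | 3 | yes | 0 |
| Man, 16.5 to 14.0 | 2.5 | 3 | yes | 0 |
| Man, 15.5 to 13.4 | 2.1 | 3 | no | 3 |
| Man, 15.2 to 13.4 | 1.8 | 2 | no | 2 |
| Man, 14.0 to 13.4 | 0.6 | 1 | no | 1 |
| Woman, 14.6 to 12.3 | 2.3 | 3 | yes | 0 |
| Woman, 12.6 to 11.9 | 0.7 | 1 | no | 1 |

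An in-range Grade 4 fall needs a baseline of at least 13.5 + 5.1 = 18.6 (men) or 12.0 + 5.1 = 17.1 (women), so it is practically absent.

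**2. What a score of 0 switches off.** The repeat needs Grade 2, the clinical-significance classification Grade 1, mandatory adverse event entry Grade 3, and the pause count Grade 3. None is reached, and the SMC's scores show 0.

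**3. When hemoglobin is next measured.** Footnote i of Table 6-1 limits Visits 3, 3a and 6 to "A subset of safety laboratory test values for albumin, bilirubin (total and direct), prothrombin time, partial thromboplastin time" and three liver enzymes, so hemoglobin is not repeated there. From the Day 7 (+3) visit to the Day 28 (+7) visit is 28 − 10 = 18 to 35 − 7 = 28 days, against at most 10 days for a value graded 2 or higher. After Visit 2 the next value is Visit 4, the day of the second vaccination. After Visit 5 it is Visit 7, later than the data used for escalation.

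**4. How often such falls end in range.** Simulation, with all distributions assumed: true level T is Normal with mean and SD of 15.0 and 0.8 or 15.5 and 0.9 (men), 13.4 and 0.8 or 13.8 and 0.9 (women). Within-subject SD is 0.4, 0.5 or 0.6, and values are rounded to 0.1. The screening value is at or above the lower limit L (exclusion criterion 29). With true fall d and independent errors e, baseline B = T + e1 and follow-up F = T − d + e2. The share is p = P(F ≥ L, given B − F ≥ 2.1). A repeat G = T − d + e3 confirms if B − G ≥ 2.1.

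| True fall d (g/dL) | Share in range, men | Share in range, women | In-range falls confirmed on repeat |
|---|---|---|---|
| 0 | 70–86% | 66–80% | 3–14% |
| 1.0 | 45–68% | 41–61% | 23–41% |
| 2.5 | 12–29% | 10–22% | 84–89% |
| 3.0 | 5–16% | 4–12% | 93–97% |
| 3.5 | 1–8% | 1–6% | 98–99.7% |

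With lower limits of 13.0 to 14.0 (men) and 11.5 to 12.3 (women), the share for both sexes together becomes 4–48% at 2.5, 1–31% at 3.0 and 0.3–18% at 3.5. A second set of assumptions (limits 13.2 or 13.6 and 11.6 or 12.1, between-subject SD 0.8 to 1.2) gives 38–84% for true mean falls of 0 to 1.0.

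**5. Effect on a two-event count.** Suppose exactly two subjects in a cohort show such falls, each with a true fall of 2.5. Both are counted with probability (1 − p)²: from (1 − 0.289)² = 0.51 to (1 − 0.098)² = 0.81, before the relatedness condition. This is conditional. The documents give no rate of such falls, so no absolute pause probability follows.

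**The case against.** **This is a precedence rule, not a slip.** It is stated three times, and the table footnote calls its values guidelines that depend on institutional norms. Without it, any small decrease would be Grade 1. All of this stands. A reader might infer that the protocol contradicts itself, but it does not: it says which rule wins. What remains is that the rule is drawn too widely for large falls. The change rows still work out of range, where a man going from 15.5 to 13.4 moves from Grade 1 to Grade 3.

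**Other routes exist.** Section 3.5 has visit staff review new laboratory results and identify tests to repeat, with no grade threshold. Section 3.3.1 allows vaccination to be withheld for a clinically significant laboratory change. Section 3.4.2.1 has the internal safety team review laboratory results, and gives the SMC cumulative results. Section 3.5.8 allows adverse event entry on judgment, and Section 3.4.2.2 allows an ad hoc SMC meeting. Sections 3.6.5 and 3.6.5.2 list all data and present change from baseline. So it would be wrong to infer that nothing can prompt action, or that action can only come after the second dose. But every route that could act on a subject in time is discretionary, and none can put the result into the pause count, which needs a Grade 3 score.

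**The rule mostly filters noise.** This is partly right. In-range results predominate where the true fall is small and a repeat would usually not confirm it.

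**The laboratory manual may deal with it.** Section 6.3 refers to the manual for ranges and grades, and it is not shown. But the same section confines grading to out-of-range values, so a manual that restored these rows would conflict with the protocol.

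**Same-day sampling at Visit 4 is not caused by this rule.** That stands. It applies equally to graded values.

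**Conclusion.** The point holds as a minor one, for one analyte. The override, the reversed order of grades and the loss of the score-based steps follow from the protocol text. Only the worked cases need an assumed lower limit.

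The reach cannot be fixed from the documents. Two opposite readings are tempting, and neither is supported in general. One is that only a minority of such falls is affected: that holds for true falls of 2.5 g/dL or more at limits of 13.5 and 12.0, not for small ones. The other is that most serious falls are lost: the 41–86% in step 4 belongs to true falls of 0 to 1.0 g/dL, where most in-range cases would not be confirmed. For true falls of 2.5 or more at those limits, most already score Grade 3.

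**What to change.** In Sections 3.5.7.4, 3.5.8 and 6.3, and in the laboratory manual:

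- Keep in-range = 0 for hemoglobin falls below 2.1 g/dL. The ordering anomaly for falls of 1.6 to 2.0 then remains, and should be accepted.
- For an in-range fall of 2.1 g/dL or more from Visit 1, require a repeat within the existing 10-day window, and before the second vaccination if seen at Visit 2. Counted from the visit, that is feasible: at latest Day 10 + 10 = Day 20, before Day 28.
- If the repeat also shows a fall of 2.1 g/dL or more, apply the change-row grade for adverse event entry, SMC scores and the pause count, still subject to the relatedness condition.
- Tabulate the maximum hemoglobin fall by Table 6-4 band and treatment group, regardless of range.

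The cost is a few sentences, one table from data already collected, an occasional extra blood draw and a small chance of a confirmed noise grade. In the same simulation over Visits 2, 4, 5 and 7 with no true change, 0.04–2.2% of subjects would need a repeat and 0.001–0.3% would get a confirmed grade. Two or more of 30 would do so with probability at most 0.4%. With an assumed decline from blood sampling of 0.1, 0.2, 0.3 and 0.4 g/dL at those visits, the figures are 0.2–4.5%, 0.01–0.9% and at most 2.8%. One asymmetry is accepted: an in-range fall needs confirmation before grading, and an out-of-range one does not.

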### **3.5.9 Vital Sign Measurements**

Vital sign measurements will include systolic and diastolic blood pressures, heart rate, respiratory rate, and body temperature (which is classified as a solicited systemic event). The subject will be seated for at least 5 minutes before all measurements are taken. Vital signs will be measured in Part A at the time points indicated in the schedule of events ([Table 6-1](#)).

When procedures overlap and are scheduled to occur at the same time point, the order of procedures should be vital sign measurements and then the blood collection.

If any of the vital sign measurements meet the toxicity grading criteria for clinical abnormalities ([Table 6-3](#)) of Grade 3 or higher, the abnormal value and grade will be documented on the AE page of the eCRF (unless there is another known cause of the abnormality and that would result in an AE classification). The investigator will continue to monitor the subject with additional assessments until the value has reached the reference range,

the value at Screening, is considered stable, or until the investigator determines that follow-up is no longer medically necessary.

### **3.5.10 Physical Examinations**

In Part A, a full physical examination will be performed at Screening and a symptom-directed (targeted) physical examination will be performed at all other scheduled time points indicated in the schedule of events (Table 6-1). The full examination will include assessment of skin, head, ears, eyes, nose, throat, neck, thyroid, lungs, heart, cardiovascular, abdomen, lymph nodes, and musculoskeletal system/extremities. Interim physical examinations will be performed at the discretion of the investigator, if necessary, to evaluate AEs or clinical laboratory abnormalities. Prior to vaccination and at 7 days following vaccination, a physical evaluation of the arm that was vaccinated and the associated lymph nodes should be evaluated.

Height and weight will be measured and body mass index will be calculated at Screening only.

## **3.6 Statistical Analysis Plans**

### **3.6.1 Safety Endpoints**

The following are the safety (primary) endpoints:

#### **Part A:**

- Solicited AEs with toxicity scoring (local and systemic reactogenicity events) collected for 7 days following each vaccination
- Unsolicited AEs collected for 28 days following each vaccination; additional classification if serious, medically attended, leading to study withdrawal, or an AESI
- Safety laboratory test results with toxicity scoring (hematology, serum chemistry, and coagulation) collected at Baseline and 7 (+3) days and 28 (+7) days following each vaccination
- Urinalysis test results with toxicity scoring collected at Baseline and 7 (+3) days following each vaccination

- A subset of safety laboratory test results (as specified in [Table 6-1](#)) with toxicity scoring collected additionally at 17 ( $\pm 3$ ) days following each vaccination and 21 (+3) days (sentinel subjects) following the first vaccination
- Vital sign measurements with toxicity scoring on day of vaccination and 7 and 28 days following each vaccination

**Part B:**

- AESIs and SAEs through 1 year (or until resolved, whichever occurs first) following the last vaccination

**3.6.2 Immunogenicity Endpoints**

The immunogenicity assessments (cellular and humoral) are as follows:

**Part A:**

- Neutralizing serum antibody titers (PRNT50) to Zika (Baseline [pre-vaccination at Visit 1] and at 28 days following each vaccination [Visits 4 and 7, respectively])
- Neutralizing serum antibody titers (PRNT50) to yellow fever (Baseline [pre-vaccination at Visit 1] and at 28 days following each vaccination [Visits 4 and 7, respectively]) in the flavivirus-seropositive group
- T-cell response (cytokine activation to IFN $\gamma$  or other cytokines) (Baseline [pre-vaccination at Visit 1] and at 7 days following each vaccination [Visits 2 and 5, respectively]), if results of interim immunogenicity analyses warrant further analyses of samples.

**Part B:**

**3.6.3 Neutralizing serum antibody titers (PRNT50) to Zika virus at 168 ( $\pm 15$ ) days and 364 (+15) days (Visits 12 and 19, respectively) following the second vaccination will be evaluated if interim immunogenicity analyses warrants long term analyses of persistence. Sample Size Calculations**

Approximately 90 subjects are planned to be randomly assigned to receive study treatment. Formal sample size calculations were not performed. The number of subjects was chosen based on feasibility and is considered sufficient to meet the study objectives of identifying a dose and establishing initial safety results in a population of healthy adults in a non-endemic Zika region.

**3.6.4 Analysis Sets**

The All Enrolled Subjects set will include subjects who signed the ICF. The All Enrolled Subjects set will only be used for descriptive purposes.

The Safety set will include all subjects who receive at least 1 dose of study drug (mRNA-1325 or placebo). All subjects in the Safety set will be analyzed according to the study drug actually received and not according to the study drug the subject was randomized to receive, in the event there is a discrepancy.

The Per-Protocol set will include all subjects who did not observe a major protocol violation, received vaccine within the acceptable vaccination window (their full dose[s] of assigned study drug), had blood collection within accepted visit windows, and had a pre-vaccination and at least 1 serum sample from the post-vaccination testing period available for testing. All subjects in the Per-Protocol set will be analyzed according to the study drug the subject was randomized to receive and not according to what was actually received, in the event there is a discrepancy. In the case where there is not a paired sample for the specific time point that data will not be included in the analysis.

The Intent-to-Treat set will provide supportive analyses. For the Intent-to-Treat set, all subjects who were randomized to the study will be included regardless of protocol violations, exceeded visit windows, missed vaccination, or missing data.

